9.4. Randomisation

Participants will be randomised once informed consent has been gained. A randomisation list will be generated using the web-based randomisation system Sealed Envelope¹⁷ by an independent researcher

at the study site who is not part of the study team. Randomisation will be stratified by arthroplasty type. Permuted block randomisation will be used to ensure the strata are balanced between the groups. The independent researcher will then follow the sequence list generated to write each individual allocation in an opaque sealed envelope which will be labelled on the outside in number order from 1-20 with each stratum beside it (knee or hip arthroplasty). When a participant has completed the baseline study assessment a second independent researcher will take the opaque sealed envelope in number sequence, based on the participant's type of arthroplasty, to determine that participant's treatment allocation. This treatment allocation will then be passed onto the treating physiotherapist via a referral form and the participant will be informed of their group allocation when they attend their physiotherapy sessions. The second independent researcher will also complete a randomisation log to document each participant's allocation.

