3. SYNOPSIS

Study Title	A Backwards Walking Programme following Hip and Knee Arthroplasty: A Feasibility Pilot Study		
Internal ref. no. / short title	Backwards Walking in patients following Knee and Hip Replacement		
Study registration			
Sponsor	Oxford University Hospitals NHS Foundation Trust		
Funder	N/A		
Study Design	Mixed methods feasibility pilot study		
Study Participants	Men and women who have undergone hip or knee arthroplasty		
Sample Size	40 participants/ 20 per group		
Planned Study Period	12 months total length/ individual participant involvement 3 months		
Planned Recruitment period	01/03/2020 to 01/09/2020		
	Objectives	Outcome Measures	Time point(s)
Primary	To test the procedures and processes of the trial and to estimate parameters for the main trial sample size calculation	
 • Berg Balance Scale • Participant recruitment figures • Participant retention figures • Number of protocol violations • BW programme diary • Qualitative interviews 	Baseline and 3 months
Secondary	To examine the consistency of the effects of the backwards walking programme on falls risk, balance, strength and gait speed following hip and knee joint arthroplasty	
 • Four Square Step Test • 2 minute walk test • 30 second stand test • Activities-specific Balance confidence scale • Falls diary 	Baseline and 3 months
Intervention(s)	A 12 week backward walking programme alongside a standard course of physiotherapy		
Comparator	Standard course of physiotherapy		

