7. STUDY DESIGN

This study is a mixed methods design. The quantitative study will be a randomised single blinded design. Up to 40 participants will be recruited from a single site at the Nuffield Orthopaedic Centre in Oxford. After recruitment baseline outcome measures will be taken. Block randomisation will then be used to balance stratification factors (hip or knee arthroplasty) into either the intervention or control group. The participant will receive their physiotherapy intervention or control at the Nuffield Orthopaedic Centre which will last up to 12 weeks. Once the first 5 participants randomised into the intervention arm have been recruited the study will be halted whilst all adverse event data is collected to ensure participants have not fallen when completing the intervention. If the study team is happy the intervention is not causing any adverse events, then the next five participants will be recruited and again the study will halt whilst their adverse event data is collected. This will continue until all 20 participants for the intervention group are recruited. Outcome measures will be repeated at 12 weeks once the treatment has ceased. This will be the final data collection point for the study.

The qualitative element of the study will involve semi structured interviews. This will take place after the participants have completed their 12 week follow up and physiotherapists have completed the intervention delivery. We will interview to a point of theoretical saturation¹⁶, and anticipate that up to 10 participants and 5 physiotherapists will allow us to develop useful themes.

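### Does the plan need to say whether 20 hip and 20 knee envelopes form a quota, and what happens when one set is used up?

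*Combined protocol and SAP*

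**What the plan says.** Section 9.4 stratifies by arthroplasty type and uses permuted blocks; the block size is not given. Allocations go into opaque envelopes "labelled on the outside in number order from 1-20 with each stratum beside it (knee or hip arthroplasty"). After the baseline assessment, "a second independent researcher will take the opaque sealed envelope in number sequence", choosing by the participant's joint. "The second independent researcher will also complete a randomisation log to document each participant's allocation".

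The size targets concern the total and the treatment arms. The synopsis gives "40 participants/ 20 per group", and section 11.3 repeats it. Section 7 says "Up to 40 participants will be recruited from a single site". It also sets a pause for safety data: "Once the first 5 participants randomised into the intervention arm have been recruited the study will be halted". The cycle repeats for every five intervention participants: "This will continue until all 20 participants for the intervention group are recruited".

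Sections 8.2 and 8.3 admit either joint and set no limit per joint. Section 11.2 collects the numbers screened and the reasons for not entering the trial.

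**The concern.** One series of 20 envelopes could not serve 40 people, so the natural reading is two series, one for hips and one for knees. Together they hold exactly 40, and all 40 people can be allocated only if the joints split 20/20. Nothing sets that split as a target: the 20 per group refers to treatment arms, and the blocks balance the arms within each joint without fixing how many hips and knees enter.

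If no cap is meant, the commoner joint will usually exhaust its envelopes first. Because the envelope is drawn after consent and baseline measures, an eligible person might be assessed and then have no allocation waiting. Staff would have to improvise. If a cap is meant, some willing patients may be turned away for a reason the protocol does not name, in a pilot whose purpose includes testing procedures and recruitment.

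**Working it through.** **Envelope supply.** 2 strata × 20 = 40 and 2 arms × 20 = 40, so two series reproduce the planned total. A single series gives 20 and does not.

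**Inputs.** N = 40 (sections 3, 7 and 11.3). The site's hip/knee mix is not given, so three knee shares p are used: 0.50; the national share from section 5, 102,944 / (97,792 + 102,944) = 0.513; and an assumed 0.60. Joints are taken to arrive independently.

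**If there is no cap.** Let X ~ Binomial(40, p) be the number of knees among 40 consecutive participants. A series runs out unless X = 20, so P(run-out) = 1 − C(40,20) p^20 (1−p)^20. The mean number without an envelope is E[max(X, 40−X)] − 20.

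| Knee share | P(exactly 20/20) | P(run-out) | Mean without an envelope |
|---|---|---|---|
| 0.50 | 0.1254 | 0.8746 | 2.51 |
| 0.513 | 0.1237 | 0.8763 | 2.54 |
| 0.60 | 0.0554 | 0.9446 | 4.29 |

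The first person to meet an empty series is, at the median, the 37th participant (35th at 60:40). If recruitment ends at 38, P(run-out) falls to 0.627 (0.819 at 60:40); at 36 it is 0.405 (0.669).

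**Effect on the quantitative aim.** Section 11.2 uses the Berg Balance Scale standard deviation to size the main trial. Under a normal approximation with complete data, the relative standard error of a pooled two-arm standard deviation is about 1/√(2(n−2)):

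- n = 40: 1/√76 = 11.5%
- n = 40 − 2.5 = 37.5: 1/√71 = 11.9%
- n = 40 − 4.3 = 35.7: 1/√67.4 = 12.2%

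Even if all recruitment stopped at the first empty series, the mean number randomised would be 35.9 (33.4 at 60:40), giving 1/√67.8 = 12.1% (1/√62.8 = 12.6%).

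**Warning before run-out.** In simulation with assumed blocks of 4, the pause after 15 intervention participants falls at about the 29th randomisation. A series has run out by then in about 4% of trials at 50:50 and 16% at 60:40.

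**If 20 per joint is a cap.** Filling both series would take on average 45.0 willing, eligible patients at 50:50, or 50.6 at 60:40. A cap does not oblige the site to fill both, since section 7 sets 40 as a maximum. The recruitment period is "01/03/2020 to 01/09/2020", but neither an accrual rate nor the length of the pauses is given, so the documents support no estimate of delay in days.

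**If each series ran to 40 instead.** With assumed blocks of 4 and a stop at 40 overall, the arms would be exactly 20:20 in 62.5% of trials and always within 18–22. Two full series of 20 give exactly 20:20 whenever the block size divides 20.

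**The case for a change.** The best case for a change is that the omission is real, settling it costs little, and procedures are what this pilot tests. Section 9.2 ties eligibility to the section 8 criteria, where a full stratum is no bar, so someone could consent, complete the baseline measures and find no envelope. Drawing from the other joint's series would weaken the stratification. Turning patients away under an unstated cap would affect the recruitment figures meant to inform the larger trial.

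The omission stands, and a line in the site's working instructions would do no harm. The consequences shrink on inspection. A shortage may surface after baseline, but it need not: the joint is an entry criterion checked from the notes at screening, and the remaining envelopes can be counted at any time. The safety pauses are natural occasions for that count, though a coarse safeguard: at the third pause the fuller series has a median of 3 envelopes left (50:50, blocks of 4), with about 11 participants to come. Screening may also precede randomisation by up to 2 months, so a check is most useful just before consent is booked. A patient turned away for this reason can be counted under the reasons for non-entry that section 11.2 already collects. Even an envelope borrowed from the other joint is still a concealed random allocation; only the balance within joint suffers, for a few late participants.

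**Conclusion.** No change to the plan is needed. Section 9.4 leaves a practical rule unwritten, and the text does not show whether a cap was intended. Either sensible course works: treat 20 per joint as a cap, or have the independent researcher extend the list. The choice is a fair trade-off. A cap protects the 20:20 arms and the count of 20 intervention participants in section 7, at the price of turning some patients away. Longer series admit everyone up to 40, but the arms may end slightly uneven.

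The 87% (94%) chance of run-out sounds large, but it applies only if there is no cap, 40 people arrive in sequence and nobody extends the list. Behind it lie about 2.5 (4.3) people of 40, all late in recruitment. Running out depends on the order in which joints arrive, so earlier allocations are untouched. Section 11.2 is descriptive and does not aim to measure efficacy; the precision of the one standard deviation it needs moves by less than one percentage point at those mean shortfalls. These figures rest on the two-series reading, independent arrivals, an assumed joint mix and, where stated, assumed blocks of 4.

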9.5. Blinding and code-breaking

The trial research clinician who is completing the study assessments will remain blinded to the participant allocation and will not be involved in any part of the randomisation procedure to ensure that they are not able to bias the group allocation. Due to the nature of the intervention it is not possible to blind the participant or treating clinician.

As participants and treating clinicians are not blinded to the treatment allocation it is not necessary to have a code-breaking procedure.

9.6. Description of study intervention(s), comparators and study procedures (clinical)

9.6.1. Description of study intervention(s)

This group will undertake a routine course of one to one out-patient physiotherapy which will include a BW programme. The BW programme will be prescribed by a physiotherapist and the participant will carry it out, along with other prescribed exercises, in their own home. Aside from the BW programme the physiotherapy treatments offered in the initial and review sessions will not be restricted but will be recorded in treatment logs. Each participant will initially be prescribed a 5 minute BW programme to be completed once a day. Participants will score the intensity of their backwards walking based on the BORG rating of perceived exertion scale. The aim will be for participants to be working at the light to somewhat hard level on the scale (11-14) (see appendix 1). The length of the BW programme and intensity will be progressed or regressed as deemed appropriate by the treating clinician with the aim for patients to achieve at least 10 minutes of BW every day of the week by the end of the programme. The

programme will be issued for completion over the course of 12 weeks and up to four review appointments will be made with the participant to monitor the BW programme and other prescribed exercises. To promote adherence a BW programme diary will be issued to participants to complete each time they carry out the programme in their own homes.

The intervention was developed in line with the MRC developing complex intervention guidelines¹⁸. The guidelines state a three stage process should be used to develop interventions including identifying existing evidence, identifying and developing theory and modelling process and outcomes. The initial stage of identifying evidence was conducted by reviewing a recent literature review which appraised 11 studies with a backwards walking programme for musculoskeletal conditions¹³. The studies ran over no more than 4 weeks and each session lasted between 5 to 10 minutes. From this we surmised that as these patients would have recently had joint replacement surgery they may struggle with the intensity of a 10 minute programme used in other musculoskeletal conditions. It was determined therefore that initially the sessions should start at 5 minutes and that the treating therapists should clinically reason when to progress each participant up to the maximum 10 minute BW programme. All the studies were conducted in a supervised environment with some participants returning daily to complete the BW programme under supervision. This was not deemed feasible in an NHS setting where clinical resources are limited and so along with consultation from clinical specialists it was determined that the programme should initially be prescribed by a physiotherapist and once the patient could complete this safely this should be issued for completion at home over 12 weeks. This formed the identifying and developing theory process. The final stage is modelling and outcomes which will be tested in this feasibility pilot study.

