6. OBJECTIVES AND OUTCOME MEASURES

Objectives	Outcome Measures	Timepoint(s) of evaluation of this outcome measure (if applicable)

Primary Objective To test the procedures and processes of the trial and to estimate parameters for the main trial sample size calculation
	
 • Berg Balance Scale (BBS) (to calculate sample size) – Static and dynamic balance activities of varying difficulty are performed to provide a measure of falls risk and balance • Participant recruitment figures • Participant retention figures • Randomisation acceptability • Number of protocol violations from fidelity checks • BW programme diary to provide a measure of adherence • Participant safety through recording any falls and injuries whilst completing the BW programme • Qualitative interviews to determine acceptability of intervention and delivery with participants and physiotherapists 	Baseline and 3 months

Secondary Objectives To examine the consistency of the effects of the backwards walking programme on falls risk, balance, strength and gait speed following hip and knee joint arthroplasty
	
 • Four Square Step Test (FSST)- a test of dynamic balance that clinically assesses a person's ability to step over objects forward, sideways, and backwards • 2 minute walk test (2MWT)- assesses walking distance • 30 second chair rise test - assesses sit to stand ability and provides a measure of lower limb strength and dynamic balance. • Activities-specific Balance confidence scale (ABC) - self-reported measure of confidence in performing various ambulatory activities without falling • Falls diary - records the frequency of falls 	Baseline and 3 months

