14. PROTOCOL DEVIATIONS

A study related deviation is a departure from the ethically approved study protocol or other study document or process (e.g. consent process or administration of study intervention) or from Good Clinical Practice (GCP) or any applicable regulatory requirements. Any deviations from the protocol will be documented in a protocol deviation form and filed in the study master file.

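### Does Section 9.6.1 contradict itself by making 10 minutes of backwards walking both a daily minimum and a maximum?

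*Combined protocol and SAP*

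**What the plan says.** Section 9.6.1 of the combined protocol and SAP speaks about the length of the backwards walking (BW) programme in two places.

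- **What will be prescribed.** Participants will "initially be prescribed a 5 minute BW programme to be completed once a day". Length and intensity are then "progressed or regressed as deemed appropriate by the treating clinician", the aim being that they "achieve at least 10 minutes of BW every day of the week by the end of the programme". This part states no upper limit.
- **How the intervention was developed.** The section reports that in the reviewed studies "each session lasted between 5 to 10 minutes". It explains the choice of a 5 minute start by the recent surgery, and says that therapists should "clinically reason when to progress each participant up to the maximum 10 minute BW programme".

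Two other sections bear on the consequences. Section 14 includes departures in the "consent process or administration of study intervention" among deviations and adds: "Any deviations from the protocol will be documented in a protocol deviation form and filed in the study master file". Section 6 lists "Number of protocol violations from fidelity checks" under the primary objective.

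**The concern.** Read literally, the first statement sets a floor with no ceiling and the second sets a ceiling. A therapist who asks whether a participant may go past 10 minutes finds two answers in the definition of the component that separates the two arms. The second statement cannot be dismissed at once as history: it says what therapists should do for each participant, and the 5 minute start decided in the same sentence reappears as an operating rule.

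At stake would be the consistency of the intervention and of the deviation record. A prescription above 10 minutes would need a Section 14 form if 10 minutes is a limit, and none if it is only an aim. If fidelity checks score duration, the same prescription could also be counted either way in an outcome listed under the primary objective.

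**Working it through.** The plan gives no figure to reproduce here. The check is whether both statements can be met together, and then whether any planned result depends on the difference.

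**Step 1: can both be met?** Let *d* be minutes of BW a day and *k* the number of sessions a day.

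- Aim (Section 9.6.1, prescription text): *d* ≥ 10.
- Maximum read per session (Section 9.6.1, development text): *d* ≤ 10*k*.
- Maximum read per day: *d* ≤ 10 for any *k*.

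| Reading of the maximum | Sessions a day | Minutes a day meeting both | Minutes a week |
|---|---|---|---|
| Per session | *k* = 1 | 10 only | 10 × 7 = 70 |
| Per session | *k* = 2 (assumption) | 10 to 20 | 70 to 140 |
| Per day | any | 10 only | 70 |

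Once a day is the only frequency stated, and it is attached to the starting prescription. The text names length and intensity as the things to be progressed, not frequency, so *k* = 2 is a possible reading and not a stated one. On every row 10 minutes a day meets both statements. At one session a day, the statements part only above 10 minutes.

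**Step 2: how many participants could be affected?** Section 11.3 plans 20 per group, so the bound is 0 to 20. The documents give nothing from which to estimate a number inside it.

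**Step 3: does any planned result depend on the answer?**

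- *BBS mean and SD, and the main-trial sample size* (Section 11.2): calculated from the observed scores in the same way on either reading.
- *Recruitment, retention and acceptability of randomisation*: no link to the upper end of BW duration in how they are measured.
- *Adherence*: Section 11.2 measures it against the programme prescribed to the participant, so its reference point is the therapist's prescription and not 10 minutes.
- *Section 14 forms*: affected only if (a) someone is prescribed more than 10 minutes and (b) the development text is treated as a limit.
- *Violations found by fidelity checks* (Section 6): these need (a), (b) and also (c), that the checks score duration. The documents do not say that they do. Section 9.8 places the checks midway, at about 20 participants randomised, and Section 11.2 describes them as observation of treatment sessions, whereas the BW programme is done at home. Observation might show what was prescribed but would not directly measure minutes walked at home.

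The synopsis lists protocol violations without naming fidelity checks as their source. On that wider wording (a) and (b) would be enough. Even so, the plan attaches no threshold to the count, so a few forms more or fewer would not reverse a pre-stated decision.

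**The case for a change.** The strongest case for acting is that the inconsistency is on the page, in the section that defines the intervention, and one sentence would remove it. The usual ways of explaining it away each fall short. The sentence with the maximum is worded as a direction to therapists. The per-session reading needs a frequency that the protocol never provides for. Calling the floor an aim does not settle whether going past it is permitted. The development text also shows concern that recently operated patients might find a 10 minute programme hard, so duration was a considered point.

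The textual part of this stands: the statements differ, and neither is marked as governing. What does not stand is the step from there to a consequence for the trial. The development text is a past-tense account, and its maximum follows closely on a report of sessions of 5 to 10 minutes in earlier studies, so it may simply name the top of that range. The concern about patients struggling is used there to explain the shorter start; it is not given as a reason for a cap. The aim is subject to the treating clinician's judgement and directs nobody beyond 10 minutes, so a therapist following either text works towards the same figure. The disagreement is over a permission inferred from the wording of the aim.

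**Conclusion.** This is an ambiguity of wording and not a flaw in the design or analysis. Ten minutes once a day meets both statements. The gap opens only above that figure, for an unknown number between 0 and 20 participants, and no effect on any trial outcome, including the violation count, can be shown from the documents. Following the plan as written would still give usable recruitment, retention, adherence and SD estimates.

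The conclusion rests on three points: adherence is judged against the individual prescription, as Section 11.2 says; the documents do not make duration a fidelity item; and no decision rule is tied to the number of violations. If the study team did intend to score duration, it would need one agreed reading before doing so.

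The two statements should be reconciled when the text is next edited, making clear whether 10 minutes is an aim or a limit and whether it applies per session or per day. Which reading is right is for the clinical team. It is an editorial clarification, and no sample size, visit, data item or analysis depends on it.

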30s Chair rise test – This is a validated clinical measure of lower body strength and dynamic balance which is recommended as one of the best physical performance tests following joint arthroplasty by OARSI²². The participant is asked to sit in a straight back chair of 17" seat height without arms. From the sitting position, the participant stands up completely up so hips and knees are fully extended, then completely back down, so that the bottom fully touches the seat. This is repeated for 30 seconds and the participant should not use their hands to get up. If the participant is unable to do this they are allowed to place their hands on their knees or use their regular mobility aid to rise from the chair and this is recorded as an adapted score.

Following the collection of the physical outcome measures the participants will be asked to complete the ABC questionnaire. This provides a measure of balance confidence whilst performing certain tasks and is a 16 item self-report measure. Each question is scored out of 100 with 0 representing no confidence and 100 representing total confidence. The average of all scores is used to provide a final score and normative data is available for older adults²³.

At the end of the assessment the participant will be issued with a falls diary to complete for the 3 months whilst they are taking part in the study. For those randomised to the intervention arm a diary of adherence to the BW programme will also be issued at the initial physiotherapy appointment.

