9.8. Subsequent Visits

As this is a feasibility pilot study the main aims are not to assess the effectiveness of the intervention but to trial the acceptability and feasibility of the study protocol and pilot its delivery at the Nuffield Orthopaedic Centre in Oxford. For this reason the main assessments for the study relate to recruitment, retention and acceptability. The research clinician will therefore collect data throughout the trial on the number of patients screened, the number that consented, the reason for not consenting, the number of drop outs, the availability of the outcome measure data and the standard deviation of the BBS in order to estimate the sample size. The acceptability of the intervention will be measured through collection of the BW programme diary which will provide a measure of adherence. Participants will also be invited to take part in an interview to determine the study acceptability.

Fidelity checks

Fidelity checks will be made by a member of the study team who is not blinded to treatment allocation to ensure adherence to the study protocol from the recruiting and treating clinicians. These will take place mid-way through study recruitment once approximately 20 participants have been randomised.

12 week follow up

Participants will be followed up at 12 weeks for the final assessment. Participants will be asked to return to the physiotherapy clinic or where possible this appointment will tie in with their final physiotherapy appointment at 12 weeks. The outcome measure assessments will be the same as at baseline and the research clinician will ensure they collect in the falls diary and if applicable BW programme diary.

Qualitative interviews

Patients taking part in the study, and treating clinicians, will be invited to take part at the in a semi-structured interview to determine if the study procedures and trial design were acceptable to participants. This will take place after the participants have completed their 12 week follow up and physiotherapists have completed the intervention delivery.

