11.2. Description of the Statistical Methods

This is a feasibility pilot RCT, therefore the aim of this study is not to provide a measure of efficacy but to determine whether it is possible to run a large scale RCT. Participant demographics will be summarised using standard descriptive statistics. The following components will also be analysed:

- The mean and SD of the primary outcome measure the BBS will be analysed to provide a sample size calculation for a larger RCT
- Recruitment – The number of recruited participants in the recruitment window, the number of participants screened to allow for the recruitment target to be met and the reason for non-entry into the trial which will provide realistic expectations of recruitment for a future larger scale RCT.
- Randomisation – Is randomisation acceptable to participants in this study? Does randomisation create comparable groups?
- Intervention acceptability – Is the intervention acceptable to participants? Do any participants fail to complete the intervention? Adherence to the prescribed BW programme will be measured through a collection of a diary. These issues will also be explored in more depth as part of the qualitative study.
- Retention of participants – Drop outs and wherever possible the reason for drop out will be recorded.
- Fidelity - Fidelity checks will be conducted, this will involve observing treatment sessions to check adherence to the protocol.

Qualitative interviews:

The data from the interviews will be analysed using thematic analysis, using six steps proposed by Braun and Clarke transcribing the data, generating initial codes, searching for themes, reviewing themes, defining and naming themes and producing the report. Data will be transcribed from the audio recordings, whilst initial ideas are recorded. Then data will then be coded, before codes are grouped into themes. To aid the process of data analysis NVIVO 10 (or later version) software will be used, this computer programme is designed for the analysis of qualitative data. It allows the collection, sorting and analysing of data from qualitative methods such as interviews.

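### The backward walking diary is completed only when a session is done, so a day without an entry cannot be told apart as missed or merely unrecorded

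*Combined protocol and SAP*

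**What the plan says.** Section 9.6.1 sets the schedule and the recording instruction. On the schedule: "Each participant will initially be prescribed a 5 minute BW programme to be completed once a day", with the aim of sessions "every day of the week by the end of the programme", and the "programme will be issued for completion over the course of 12 weeks". On recording: "a BW programme diary will be issued to participants to complete each time they carry out the programme in their own homes".

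Section 6 lists, under the primary objective, the "BW programme diary to provide a measure of adherence". Section 9.8 treats the same diary as the measure of intervention acceptability. Section 11.2 states: "Adherence to the prescribed BW programme will be measured through a collection of a diary".

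On handling, section 9.7 says that for the intervention arm "a diary of adherence to the BW programme will also be issued at the initial physiotherapy appointment". Section 9.8 has the research clinician, at the 12 week visit, "ensure they collect in the falls diary and if applicable BW programme diary".

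No section asks for an entry on a day without a session, defines the adherence calculation, or says how blank days or unreturned diaries are treated. The diary form is not part of the documents.

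**The concern.** A diary filled in only when something happens leaves no trace of whether it was being kept on the other days. If a participant's entries stop at week 6, the participant may have stopped walking or stopped writing, and the returned diary looks the same either way.

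This matters more here than in many exercise trials. By the plan's own account in section 9.6.1, the backward walking studies it drew on ran for no more than 4 weeks and were supervised. This study moves to 12 weeks, mostly unsupervised at home. Whether patients keep the programme up is therefore one of the main things a feasibility study should find out. Section 11.2 also asks whether any participants fail to complete the intervention. If poor diary-keeping cannot be separated from poor adherence, the main trial could be designed around the wrong problem.

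**Working it through.** The plan states no adherence figure, target or formula, so there is nothing to reproduce. The check is what the diary, as described, can and cannot establish.

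**Inputs.** Once a day and 12 weeks (section 9.6.1); 20 participants in the intervention arm (section 11.3). The share of completed sessions that get written down is not given, and the bounds below do not need it.

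**1. Prescribed sessions.** n = 12 × 7 = 84 per participant, if the prescription stays daily throughout. Over the arm, 20 × 84 = 1,680.

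**2. Which ratio can be formed.** Let k be the number of days with an entry.
- Entries over recorded days: k / k = 100% for everyone, which carries no information.
- Entries over prescribed days: k / n. This is the only informative ratio, and it counts every day without an entry as missed.

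**3. What k entries establish.** If no entry is false, at least k sessions were done, and any of the n − k blank days may hide another. True adherence lies between k/n and n/n:
- k = 42: 42/84 = 50.0%, up to 100%
- k = 59: 59/84 = 70.2%, up to 100%
- k = 76: 76/84 = 90.5%, up to 100%

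The upper limit is always 84/84, because no day is ever positively marked as not done.

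**4. Direction of error.** Let A be true adherence, r the share of completed sessions that are entered, and f the share of prescribed days with an entry but no session. Then

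k/n = A·r + f, so k/n − A = f − A(1 − r).

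Unlogged sessions pull the figure down and false entries push it up. The documents give neither r nor f, so the sign cannot be determined.

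**5. What a daily done / not done row would give.** Take an illustrative participant with 42 rows ticked *done*, 21 *not done* and 21 blank, out of 84:
- Completeness: (42 + 21)/84 = 63/84 = 75%
- Adherence among completed rows: 42/63 = 66.7%
- Lower bound, blank = not done: 42/84 = 50%
- Upper bound, blank = done: (42 + 21)/84 = 63/84 = 75%

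The interval is 25 percentage points wide (21/84), against 50 points for the same participant under the present instruction. The 66.7% lies inside the bounds; it is an estimate and not an upper limit.

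**6. Unreturned diaries.** Assume 18 of 20 diaries come back fully completed with mean adherence 80%, and 2 do not come back. Counting those two as all blank gives (18 × 0.80 + 2 × 0)/20 = 72% to (18 × 0.80 + 2 × 1)/20 = 82%.

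**The case against.** The strongest reply is that the plan never says blank days count as missed. That is right. A reader might infer that entries over 84 is the plan's method, but no section states a formula; it is a deduction from the recording instruction. The 84 is itself uncertain, because daily is what is prescribed initially, the programme may be progressed or regressed, and the diary starts only at the first physiotherapy appointment.

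Second, the form may already be a daily grid. This cannot be excluded. The lay summary mentions a tick-box diary, but it is given out at the first assessment, which by section 9.7 fits the falls diary better. Even a grid would need a *not done* box, an instruction to complete it daily, and a rule for blanks.

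Third, other information exists: at most four review appointments that monitor the programme, treatment logs, recorded reasons for withdrawal, and interviews. A reader might conclude that nothing could separate stopping from not writing, and that goes too far. A participant who had stopped could be identified at a review or interview. But no section says diary entries are checked at reviews, and interviews are expected with up to 10 participants after the 12 week follow-up. These sources give context; they do not rebuild daily data for 20 people.

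Fourth, no adherence threshold or progression criterion is set, so no stated decision turns on the figure. That limits the severity, but adherence remains an outcome under the primary objective.

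**Conclusion.** The point holds as a weakness in how adherence is recorded, with a cheap remedy. As worded, the instruction makes a blank day uninterpretable, and analysis of the diary alone cannot repair this afterwards. Its size is the width of the range left open: with k entries over n prescribed days, true adherence may lie anywhere from k/n to 100%, for example 50% to 100% with 42 of 84. This rests on no entry being false and on a daily prescription over 12 weeks.

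A reader might go further and infer that adherence will be under-reported by a definite amount. The documents do not support that. They give no logging rate, and a self-report diary collected once at 12 weeks can be back-filled or over-reported, so the net direction of bias is unknown.

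A reader might also infer that walking done at clinic visits is lost from the measure. Section 9.6.1 describes a programme carried out at home, and no section says that walking at an appointment replaces that day's home session.

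**What to change.** **Section 9.6.1.** Use a diary with one pre-printed, dated row per day carrying *done* and *not done* boxes, and ask participants to complete it every day. A blank row then means missing. If the form is already a daily grid, only the boxes and the instruction need checking.

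**Section 11.2.** Report for the intervention arm:
- diary completeness: completed rows / prescribed days;
- adherence among completed rows: done / completed rows, labelled as an estimate;
- lower bound: done / prescribed days (blank = not done);
- upper bound: (done + blank) / prescribed days (blank = done).

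Count an unreturned diary as all blank. Define prescribed days as starting at the initial physiotherapy appointment, when the diary is issued, and as following any recorded change in prescription.

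**Cost.** A reformatted diary, a short addition to section 11.2, and one extra tick on days without a session. The change has to be made before diaries are issued.

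**What remains.** If some participants still tick only on days they walk, adherence among completed rows will read 100% for them, but low completeness and wide bounds will show it. The bounds do not cover false or back-filled entries, and the report should say so.
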